#### 13.6.2 Vital signs

Results obtained for vital sings and changes from baseline in these parameters (body temperature, respiratory rate, systolic blood pressure, diastolic blood pressure, and pulse rate) will be presented as listings and as summary data for each measurement point.

### 13.6.3 Electrocardiography

Electrocardiography findings will be presented as listings and as summary data for each measurement point. ECG intervals (QT interval, RR and QTcF) will be presented as absolute values for each measurement point and changes from baseline for each measurement point.

#### 13.6.4 Laboratory tests

Laboratory results (complete blood count, blood chemistry, blood lipids, coagulation tests, and urinalysis) will be tabulated by treatment group using descriptive statistics for each measurement point and for changes from baseline.

All laboratory results will be presented as lists with values for each teste and changes from baseline. Laboratory findings that are outside of the reference interval will be marked in the listings.

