#### 7.2 Inclusion criteria

To initiate treatment of patients with the investigational product and to carry out the investigation procedures specified by the protocol after the screening visit, patients had to meet all the inclusion criteria:

- 1. The patient gave his / her informed consent to participation in this study; the Informed Consent Form was signed both by the patient and the Investigator;
- 2. Male and female patients aged 18 to 80 years inclusive;
- 3. Established diagnosis of gout according to the criteria established by the American College of Rheumatology (ACR) and European League against Rheumatism (EULAR) in 2015;
- 4. Pain in at least one joint at the screening and immediately prior to initiation of therapy with the investigational products, with intensity of 50 mm to 100 mm on the Visual Analogue Scale (VAS);
- 5. Development of acute gout attack within 120 hours (5 days) prior to the randomization date;
- 6. A history of 1 or more acute gout attacks prior to the Screening Visit;
- 7. Patients receiving uric acid-lowering agents had to continue receiving these drugs at a stable dose for at least 4 weeks prior to enrolment to the study and throughout the study; the patients not receiving uric acid-lowering drugs might start receiving this treatment after the end of the study;
- 8. Body mass index  $\leq 40 \text{ kg/m}^2$ ;
- 9. QTcF interval  $\leq 450$  msec for menand  $\leq 470$  msec for women on ECG at screening;
- 10. For women with childbearing potential: negative serum pregnancy test at screening;

CONFIDENTIAL P. 38 of 84

- 11. Consent of women of childbearing potential and men who have female partners of childbearing potential to abstain from sexual intercourse or to use effective methods of contraception throughout the study and for 60 days after RPH-104 administration (if the patient receives RPH-104), as described in Section 9.9;
- 12. The patient's ability to fulfil the requirements of the Study Protocol, as judged by the Investigator.

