- 21. Elective surgery or major surgical intervention (minor surgical procedures, such as catheter placement or bone marrow biopsy, are not exclusion criteria) within 14 days before the first dose of the investigational medicinal product;
- 22. Current or suspected HIV-infection, HBsAg, Hepatitis C Virus antibodies (HCVAb), other acute or chronic bacterial, fungal or viral infections at the time of enrolment to the study;
- 23. Presence of any risk factors for tuberculosis based on the results of assessment using the Tuberculosis Risk Assessment Questionnaire at the screening or confirmed tuberculosis or any other infectious disease of the lungs or bronchi based on chest X-ray (2 views) findings performed within 3 months prior to the screening visit, or the need for anti-TB medications, such as isoniazid during the study;
- 24. Neutropenia, leukopenia, or thrombocytopenia determined based on the following laboratory parameters assessed at screening:
  - a. Absolute neutrophil count (ANC) below  $1.5 \times 10^9$ /L;
  - 6. White blood cell count below  $4.0 \times 10^9/L$ ;
  - B. Platelet count below  $150 \times 10^9/L$ ;
- 25. Immunization with live vaccines within 3 months prior to the subject's enrolment to the study or planned vaccination within 60 days after the expected date of the first dose of the investigational product;
- 26. A history of allergic reactions to biological drugs, Voltaren® (diclofenac) or Ortanol® (omeprazole);
- 27. Contraindications to subcutaneous, intramuscular, intravenous or intra-articular injections;
- 28. A history of malignancy (except for patients with localized *in situ* basal cell carcinoma of the skin or *in situ* cervical cancer, who could be enrolled to the study immediately after the treatment for this disease), unless it is in remission for ≥5 years, as well as patients who are investigated for cancer or patients with a suspected malignancy;
- 29. A condition or disease, which, in the Investigator's opinion, could jeopardize the patient's safety or affect the investigational product safety assessment;

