#### 12 ADVERSE EVENTS

In this study, an **adverse event** (AE) means any untoward medical event in a patient receiving the study drug that does not necessarily have a causal relationship with the drug. Thus, an adverse event can be any unintended and untoward symptom (for example, a laboratory abnormality), a symptom or a disease with temporal relationship with the use of the drug, regardless of whether they are considered to be related with the drug.

Clinical signs of treatment failure are not adverse events. For example, persistent pain or swelling in an affected joint should not be reported as an adverse event.

Symptoms, syndromes, and diseases noted prior to the study therapy, but after the patient signed the informed consent form, are recorded in the CRF as Concomitant Diseases.

Laboratory and investigation abnormalities should be registered as adverse events if these abnormalities are regarded by the investigator as clinically significant.

An **adverse drug reaction** is any adverse event with at least a possible (possible, probable, or certain) relationship with the use of the investigational medicinal product.

AE severity is graded according to the CTCAE classification v.5.0.

All adverse events should be monitored until resolution or stabilization (assessed by the investigator).

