#### 13 DATA ANALYSIS AND STATISTICAL ANALYSES

## 13.1 General provisions

Standard statistical calculations for continuous data sets will be performed to indicate the number of cases (N), mean value, standard deviation, minimum, median, and maximum. Categorical data will be reflected by the N value and proportion (%). For all registered types of data, all individual patient values will be listed.

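### Apart from adverse event records, the plan gives no count by arm of patients whose laboratory or QTcF values cross a limit after dosing

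*Combined protocol and SAP*

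**What the plan says.** Four parts of the protocol bear on this.

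- **Laboratory tests (13.6.4).** Results "will be tabulated by treatment group using descriptive statistics for each measurement point and for changes from baseline". Abnormal values are handled in one sentence: "Laboratory findings that are outside of the reference interval will be marked in the listings".
- **ECG (13.6.3).** "ECG intervals (QT interval, RR and QTcF) will be presented as absolute values for each measurement point and changes from baseline" at each measurement point. The section gives no categories and no rule for flagging, and does not state that the summary is by treatment group.
- **Descriptive statistics (13.1).** The set is "the number of cases (N), mean value, standard deviation, minimum, median, and maximum". The synopsis adds the 25th and 75th percentiles. All individual values are also listed.
- **Adverse events (12, 11.5.5, 13.6.1).** "Laboratory and investigation abnormalities should be registered as adverse events if these abnormalities are regarded by the investigator as clinically significant". Section 11.5.5 sets the same test for new ECG findings. Section 13.6.1 then reports numbers and percentages of patients with adverse events by dose.

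Numeric limits appear only as entry criteria. Section 7.3 excludes "Neutropenia, leukopenia, or thrombocytopenia determined based on the following laboratory parameters assessed at screening": neutrophils below 1.5, white cells below 4.0 and platelets below 150, all ×10^9/L. It also excludes creatinine clearance below 60 mL/min. Section 7.2 requires QTcF of at most 450 ms in men and 470 ms in women. No on-treatment limit is given for any of these.

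**The concern.** Safety is the first aim in the study title, and the study compares five doses. For laboratory values and QTcF, a basic dose-ranging question is how many patients at each dose moved out of an acceptable range. The planned laboratory and ECG summaries do not answer it. The one tabulated count runs through the adverse event record, and so through a judgement of clinical significance made with the treatment and dose known. If investigators apply that judgement differently by arm, or simply differently between the roughly 19 sites, the counts by dose reflect that as well as the drug.

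The listings are a weak substitute. Blood counts are run at site laboratories under each site's own procedure (11.5.6), so the reference interval behind the flag may differ between sites and from the entry limits. ECG intervals have no flag at all. Adverse event severity does not recover the laboratory grade either, because 12.3 maps CTCAE Grades 2 and 3 together to moderate.

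Section 4 adds that the interim report on 47 patients may become the final one, so these tables may be the only safety summary by dose that the study produces.

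**Working it through.** The plan states no figure for this point, so there is none to reproduce. The check asks what the planned outputs would reveal and what a count would add.

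**1. Which planned output gives the number of patients beyond a limit, by arm?**

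- Laboratory tables (13.6.4): no. They give N, mean, SD, median, minimum and maximum for each time point.
- ECG tables (13.6.3): no, and the arm breakdown is not stated.
- Listings (13.1, 13.6.4): individual values only, with no tabulated count.
- Adverse event tables (13.6.1): yes, but only for values judged clinically significant.

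**2. Can the number be recovered from the descriptive statistics?** Take an arm of n = 14 (Table 6.1). The following values are assumptions, not document figures: baseline neutrophils 7.0, most patients at 4.5 after dosing, and k patients at 1.2 (below the entry limit of 1.5).

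Mean change = [(14 − k) × 4.5 + k × 1.2]/14 − 7.0

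| k | Mean change | Median | Minimum |
|---|---|---|---|
| 0 | −2.50 | 4.5 | 4.5 |
| 1 | −2.74 | 4.5 | 1.2 |
| 2 | −2.97 | 4.5 | 1.2 |
| 3 | −3.21 | 4.5 | 1.2 |

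The 25th percentile also stays at 4.5 throughout. Each extra patient moves the mean by (4.5 − 1.2)/14 = 0.24.

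For QTcF, assume men at 410 ms with k at 470 ms (above the 450 ms entry limit for men). The mean is 410 + 60k/14, that is 410.0, 414.3, 418.6 and 422.9 for k = 0 to 3. The median and 75th percentile stay at 410, and the maximum is 470 for k = 1, 2 or 3.

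The minimum or maximum therefore shows that a crossing occurred, but not how many patients crossed. This does not depend on the assumed values. Because the extremes are given per time point, they also cannot show whether low values on two days belong to one patient or two.

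**3. What would a count give?** Exact (Clopper–Pearson) 95% intervals. With no events, the upper limit is 1 − 0.025^(1/n).

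- 0/14: upper limit 1 − 0.025^(1/14) = 23.2%
- 1/14 = 7.1% (0.2–33.9%)
- 2/14 = 14.3% (1.8–42.8%)
- 3/14 = 21.4% (4.7–50.8%)
- All RPH-104, n = 15 + 4 × 14 = 71. For 0/71: upper limit 1 − 0.025^(1/71) = 5.1%

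**4. How often would an arm of 14 show at least one case?** This is 1 − (1 − p)^14. For assumed true rates p of 2%, 5%, 10% and 20% it is 25%, 51%, 77% and 96%.

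**5. Are the data available?** Blood counts and creatinine are taken at screening, on Days 5, 15 and 45, and at an early-withdrawal visit. ECG is recorded at screening, on Days 5 and 45, and at early withdrawal (Table 3.1 and its notes). Counts, creatinine and ECG must be assessed before randomization, so in an eligible patient any later crossing is new since screening.

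**The case against.** The strongest reply is that little is lost. A value that matters clinically becomes an adverse event and is counted by dose. The minimum and maximum appear in every laboratory table. All values are listed, and with 14 or 15 patients per arm a reader could count by hand. The study is exploratory, with descriptive safety analysis and no decision rule that uses the missing table. Section 13.1.7 also defers detail to a separate SAP.

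Most of this stands, and it limits the point. A reader might infer that patients who cross a limit are counted in no table by arm. The documents do not support that: those judged clinically significant are counted in the adverse event tables. A reader might also infer that a severe case could pass unseen behind ordinary means. It would not, because the minimum or maximum would show it. What remains is that the number of patients is not tabulated on an objective definition, and that the count which is tabulated rests on open-label judgement. Section 6.3.2 accepts that knowing the drug may affect efficacy assessment; it does not discuss this safety judgement.

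A further tempting inference is that baseline, taken during the attack, causes the problem. It does not. The count is missing because no categorical table is planned, whatever the time of baseline. A fall shared by all arms as the attack resolves can be read against the randomized diclofenac arm.

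The deferral to the SAP cannot be checked. Section 13.5.3 defers efficacy detail explicitly and 13.6 does not, but 13.1.7 is general enough to cover safety tables.

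**Conclusion.** The point holds as a specific reporting gap that is cheap to close. Sections 13.6.3 and 13.6.4 name no count by arm, worst-value table or shift table for laboratory tests or QTcF. The only count of patients with abnormal values comes from adverse event records, made with the treatment known. Section 13.6.3 also leaves the ECG breakdown by arm unstated.

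The gap is moderate in size. A crossing would be visible through the minimum or maximum, while one, two or three patients of 14 would look the same there. The count itself would be imprecise: 0/14 still allows a rate up to 23.2%, and 0/71 up to 5.1%. These intervals assume full recruitment and widen if the study stops at 47 patients.

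The limits in 7.2 and 7.3 should not be read as the plan's own safety limits. They are entry criteria, and using them after dosing is a reporting choice. The neutrophil and QTcF values in the working are illustrative. The conclusion rests on the protocol text and would fall away if the separate SAP already contains such tables.

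**What to change.** Make three additions, in 13.6.3 and 13.6.4 or in the separate SAP before the interim data lock.

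1. **A threshold table by arm**, in the safety population by treatment received, with an all-RPH-104 column, the diclofenac arm as comparator, and exact 95% intervals. It gives n (%) of patients, among those with at least one post-dose value, whose worst post-dose value lies beyond the limits already used at entry: neutrophils, white cells, platelets and creatinine clearance below; QTcF above, by sex. State that these are descriptive reporting thresholds and not on-treatment clinical rules.
2. **A shift table** from baseline to worst post-dose CTCAE v5.0 grade for laboratory tests. The plan already grades adverse events on that scale.
3. **A statement in 13.6.3** that ECG summaries are by treatment group.

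The cost is one or two table shells, with no new data collected. The downside is small: some clinically unimportant crossings will be counted, including falls as the attack resolves. A crossing is new since screening but not thereby drug-related, so the RPH-104 columns should be read against diclofenac. The existing adverse event tables stay as they are.

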#### 13.6.5 Concomitant therapy

Data on concomitant therapy will be presented as a patient-specific listing and summary data.

CONFIDENTIAL P. 76 of 84

# 13.7 Interim data analysis

Due to the low patient recruitment rate in the study and the adverse impact of the COVID-19 pandemic on the recruitment, at the decision of the sponsor, an interim analysis of the data of 47 patients included in the study as of November 2020 will be carried out in order to assess the feasibility of continuing recruitment and further conducting the study. All patients whose data will be included in the interim analysis completed their participation in the study; follow-up is not required in the study. The interim analysis will include the efficacy, safety, pharmacokinetics and pharmacodynamics data available and verified at the time of analysis. No changes in the declared statistical methods in connection with the interim analysis are planned. The dose dependence of the pharmacokinetics and pharmacodynamics of the investigational product, as well as the main efficacy measures (reduction in pain intensity) will be studied using descriptive statistics, a confidence interval approach, and graphical methods. The safety analysis will be carried out using descriptive statistics methods. Formal testing of hypotheses is not planned in the study. In view of the exploratory nature of the study, no corrections for multiple comparisons are planned.

# 14 DATA HANDLING, DOCUMENTATION MANAGEMENT AND STORAGE

#### 14.1 Source documents

All obtained data should be first recorded in the source documentation on paper or electronic media, and only after that recorded in the CRF. It is prohibited in this study to record data directly in the CRF without first recording them in source documents, with the exception of creatinine clearance, which is calculated automatically in the CRF.

Source documents may include out-patient charts, in-patient medical records, office visit logs, patient questionnaires, laboratory and investigation reports.

The Investigator and the healthcare institution conducting the study must ensure access to the source documentation for study monitors, auditors, and inspectors, as well as representatives of the Local Ethics Committee / Institutional Review Board and inspectors of the regulatory authorities.

# 14.2 Archiving of study documentation at the study site

After completion of the study, the Investigator must continue to keep all study-related documentation (except documents that should be kept by other persons in accordance with local regulations) in a safe, secure place. This documentation should be stored so as to allow simple access if necessary for audit or inspection, and should be available for verification, along with assessment of the study conditions, auxiliary systems, and study site personnel.

Documentation may be stored only on paper, using media that can ensure long-term storage of recorded information. In this regard, source medical documents available on thermal printer paper (ECG recording or facsimile copy of a laboratory test report) should be copied to regular paper by means of photocopying. Any copy should be dated and authenticated by the study site personnel; the original thermal printer paper recording should be stored with the copy even if the original becomes illegible.

The Investigator will be notified by the sponsor of the document retention period. The minimal shelf-life is 15 years after completion of the study; it may be prolonged if permitted by the Sponsor or allowed by legislation.

The Investigator should notify the sponsor about all changes in the archiving procedure, including, but not limited to, storage of the archives outside of the healthcare institution or

CONFIDENTIAL P. 77 of 84

transfer of the property rights to the documentation in case the Investigator changes the place of employment.

CONFIDENTIAL P. 78 of 84

# 15 STUDY MONITORING AND QUALITY ASSURANCE

# 15.1 Study monitoring

Monitoring is carried out by R-Pharm JSC on behalf of the sponsor R-PHARM INTERNATIONAL LLC. Monitors and other authorized representatives of the Sponsor may contact the Investigator and visit the study site. At request, they should be allowed direct access to all study documents (CRFs of study subjects and other documents related to the study), provided that the confidentiality requirements are observed in relation to personal patient data and the inspection is conducted in accordance with applicable local regulatory requirements.

Responsibilities of the study site monitor include regular verification of the CRFs throughout the study to ensure that they meet the requirements of the Study Protocol, control of the completeness, accuracy, and consistency of the study data, as well as the compliance with the regulatory requirements and the ICH GCP guidelines.

The Investigator should assist the Monitor as much as possible and cooperate with the Monitor with the aim to resolve any problems identified during monitoring visits.

The Monitors will be provided with a separate guideline on the control of the study conduct that will contain additional instructions concerning the monitoring procedures.

# 15.2 Study quality assurance

Quality of this study will be ensured through audits conducted by representatives of the sponsor or authorized representatives. They should be allowed direct access to all study documents (CRFs of study subjects and other documents related to the study), provided that the confidentiality requirements are observed in relation to patients' personal data and the inspection is conducted in accordance with applicable local regulatory requirements.

### 16 ETHICAL ASPECTS OF THE STUDY

# 16.1 General provisions

This study is conducted in accordance with this protocol, the ethical principles set forth in the Declaration of Helsinki of the World Medical Association (last revision), and the current edition of Good Clinical Practice (ICH GCP E6), the legislation and standards of the Russian Federation: the Constitution of the Russian Federation; the current edition of Federal Law No. 61-FZ of the Russian Federation of April 12, 2010 On the circulation of medicinal products; the current edition of Federal Law No. 323-FZ of the Russian Federation of November 21, 2011 On the basics of protecting the health of citizens in the Russian Federation; Decree No. 714 of the Government of the Russian Federation of September 13, 2010 On Approval of Model Rules for Compulsory Life and Health Insurance of a Patient Participating in Clinical Trials of a Medicinal Product" (as amended on September 4, 2012); Decree No. 393 of the Government of the Russian Federation of May 18, 2011 On Amendments to the Model Rules for Compulsory Life and Health Insurance of a Patient Participating in Clinical Trials of a Medicinal Product; Order No. 703n of the Ministry of Health and Social Development of Russia of August 23, 2010 On Approval of the Notification Form for the Completion, Suspension or Termination of a Clinical Trial of a Medicinal Product for Medical Use; Order No. 774n of the Ministry of Health and Social Development of Russia of August 31, 2010 On the Ethics Council, Order No. 200n of the Ministry of Health of Russia of April 1, 2016 On Approval of Good Clinical Practice Guidelines, GOST R52379-2005 Good Clinical Practice and other applicable legislative acts.

CONFIDENTIAL P. 79 of 84

